### *Sample size*

The study will use all available data that fulfils the inclusion criteria.

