### *Timing of analyses and outcome assessments*

We will use data from the date of the first case in each country until December 31, 2020. We will use publicly available daily data for all outcomes. We will use the enforcement date on data on interventions collected from PoliMap ([www.polimap.org](http://www.polimap.org)).

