### *Study population*

The study will focus on local governments, third-tier administrative units in each country. These receive different denominations in each country, primarily called municipality, district or cantón. The eligibility criteria are (1) Spanish or Portuguese speaking countries in the

Americas; and (2) availability of open data for any of the outcomes of interest at a subnational level. A flow diagram (similar to those recommended by CONSORT guidelines) will be reported describing the number of countries and subnational units eligible and how many of them fulfilled the eligibility criteria.

We will report (as a Supplementary Table) a summary of the baseline characteristics of the local governments included in the study.

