#### *Outcome definitions*

The first outcome will be the 7-day moving average of daily confirmed cases of COVID-19/SARS-CoV-2. The second outcome is the time-varying reproductive number between the current and previous period. The third outcome is the 7-day moving average of the daily number of deaths by COVID-19 in Latin American subnational regions. For the statistical modelling, these averages will be rounded to the nearest integer. We will consider a 7-day lag as the primary lag. We will use the definition of COVID-19 case and death which is valid at any given time in each country.

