#### *Analysis methods*

The primary analysis will use interrupted time series (ITS) for each subnational unit to examine the causal effect of COVID-19 policies on primary outcomes. Interrupted time series is a widely used tool in causal inference that allows comparing trends before and after the introduction of an intervention. The counterfactual outcome is the projection of the trend in the period before the introduction of the intervention into the time period was introduced. The unit of analysis in this study is days, starting from the date of the first case.

The standard model for an ITS regression is as follows

$$(1) Y_t = \beta_0 + \beta_1 time_t + \beta_2 post_t + \beta_3 timepost_t + \beta'_4 X + \mu_t$$

where  $time_t$  is a variable which equals one at the first time point  $t$  and increases by one after each subsequent time point;  $post_t$  is a dummy variable that equals to zero prior to the introduction of the intervention ( $p$ ) and equals one for every time point thereafter;  $timepost_t$  is a variable that equals to zero until time  $p-1$ , and increases by one for each subsequent time point; and  $X$  is a vector of covariates. Coefficient  $\beta_3$  is the coefficient of interest and represents the change in slope after time  $p$ .

The validity of the ITS rests on three assumptions. Assumption 1 states that the expectation of the pre-intervention level and trends would be the same irrespective of whether the sample received the treatment. Assumption 2 states that in the absence of treatment, the outcome of interest would remain unchanged in the post-intervention period. Assumption 3 states that the time trends in the pre and post periods can be expressed as a linear combination of parameters.

Using the potential outcomes framework, the estimated effect of a policy at time  $p$  could be defined as

$$(2) \Delta_t = Y_t(1) - Y_t(0)$$

These difference could also be expressed in terms of two equations

$$(3) Y_t(1) = \alpha_0 + \alpha_1 time_t + \alpha_2 post_t + \alpha_3 timepost_t + \varepsilon_t$$

$$(4) Y_t(0) = \theta_0 + \theta_1 time_t + \theta_2 post_t + \theta_3 timepost_t + \nu_t$$

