Assumption 2. We will explicitly incorporate co-occurring interventions in a seven-day period as a combination of interventions. We will also adjust for changes in the case definition of COVID-19 cases and deaths for each of the respective outcomes. We will report in the Supplementary Appendix the exact dates considered in the analysis for each country/subnational unit and the interventions included in each intervention period.

Assumption 3. We will introduce flexible spline functions to account for seasonality and long-term trends. We will add a scale parameter, which will be the Pearson statistic divided by the residual degrees of freedom, to account for potential overdispersion (a violation of the Poisson regression assumption). We will test for autocorrelation using the Durbin-Watson tests and visual plots of the autocorrelation function and partial autocorrelation function. If there is evidence of autocorrelation, we will use the Newey-West method to obtain adjusted standard errors.

Therefore, in the final analysis, we will use Poisson regression to model the count data.. The final model is an extension of the regression described in equation 1 with the specifications described above. The model will include each of the interventions (either as single interventions or combinations of), denoted  $j = 1, \dots, J$ . This method allows estimating simultaneously the effect of several interventions. We will consider interventions implemented within a 7-day period as a combination of interventions, following previous studies. This means that the maximum number of combinations of interventions is 52,  $t = 1, \dots, 52$ . We will estimate the effect of the interventions separately when interventions are separated by at least seven consecutive days and for a maximum period of 30 days. The primary analysis will include a 7-day lag to account for the delay in the intervention to be effective, considering the incubation period of SARS-COV2.

$$(5) \ln(Y_t) = \beta_0 + \beta_{1j}time_{tj} + \beta_{2j}post_{tj} + \beta_{3j}timepost_{tj} + \mu_t$$

This model will be run at the municipal level and, therefore, we expect to run 10,000 regressions multiplied by the number of combinations of interventions at each municipal level. Coefficient  $\beta_{3j}$  is the coefficient of interest and represents the change in slope after the intervention  $j$  at period  $t$ .

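### With no minimum pre-policy period, the planned Newey-West errors hide how weak short baselines are, and their excess scatter is read as heterogeneity between municipalities

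*SAP*

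**What the plan says.** **Length of series.** Under *Sample size* the SAP states "The study will use all available data that fulfils the inclusion criteria". Under *Study population* the criteria are language and "availability of open data for any of the outcomes of interest at a subnational level". Neither criterion concerns series length or case numbers.

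**Start of series.** *Analysis methods* has "The unit of analysis in this study is days, starting from the date of the first case". *Timing of analyses and outcome assessments* has "We will use data from the date of the first case in each country until December 31, 2020". The first can be read as the municipality's first case; the second is the country's.

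**Outcome.** "The first outcome will be the 7-day moving average of daily confirmed cases of COVID-19/SARS-CoV-2", and "For the statistical modelling, these averages will be rounded to the nearest integer". Deaths are treated the same way.

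**Standard errors.** For overdispersion: "We will add a scale parameter, which will be the Pearson statistic divided by the residual degrees of freedom". For serial correlation, after Durbin-Watson tests and plots: "If there is evidence of autocorrelation, we will use the Newey-West method to obtain adjusted standard errors". No bandwidth, prewhitening or small-sample correction is given.

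**Policies.** Each break carries a 7-day lag. Policies at least seven days apart are modelled separately, and each effect is followed for at most 30 days. The municipal slope changes (beta3) are then pooled by random-effects meta-analysis, and I² above 50% leads to meta-regression. No listed sensitivity analysis varies the pre-policy length.

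**The concern.** The comparator is the projected pre-policy trend, so beta3 is only as good as that trend. One would expect the second-stage weights to discount a municipality with very few pre-policy days, but they can do so only if its standard error is honest. Newey-West is built from residuals, and a line through a few smoothed points leaves almost none. The reported error is then too small exactly where the true error is largest.

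What is at stake is mainly aim 2. Sampling scatter that the first stage does not declare is counted by the second stage as real variation between municipalities, and may then be handed to the meta-regression to explain.

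**Working it through.** **Inputs.** The documents give no pre-policy length, standard error, weight or tau, so there is no planned figure to reproduce. From the SAP: equation 5 with one intervention, a rounded 7-day average, up to 30 post-policy days, Newey-West if autocorrelated, and random-effects pooling of beta3. Assumed: 5, 20 or 100 cases/day at the policy date, log-linear growth, the Newey-West bandwidth, the tau-squared estimator, and no spline terms.

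**1. Why the pre-policy segment governs beta3.** With both a level term and a slope term after the policy, the two segments are in effect fitted separately, so beta3 is the post-policy slope minus the pre-policy slope. For n equally spaced points with independent errors of variance s², a slope has variance 12s²/(n(n²−1)). This is 12/(5×24) = 0.1s² at n = 5 and 12/(30×899) = 0.00044s² at n = 30. Smoothing softens the contrast, but the direction is the same.

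**2. Which standard error applies.** On the rounded average, the Durbin-Watson statistic was below 1.2 in 85% or more of fits in one set of runs and in 92–97% in the others. Newey-West would normally be used.

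**3. Median Newey-West SE divided by true SD of beta3** (rounded average, 20 cases/day). Setting A: Poisson variance, growth 0.08/day, true beta3 −0.08, bandwidth floor(4(n/100)^(2/9)), range over repeat runs. Setting B: variance twice the mean, growth 0.05/day, no effect, bandwidth 7.

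| Pre-policy days | A | B |
|---|---|---|
| 5 | 0.20–0.22 | 0.15 |
| 7 | 0.22–0.23 | 0.17 |
| 12 | 0.29 (one run) | not run |
| 14 | 0.32–0.33 | 0.28 |
| 21 | 0.42–0.43 | 0.38 |
| 30 | 0.50–0.54 | 0.49 |
| 60 | 0.65 | 0.59 |

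Coverage of the 95% interval in B is 28% at 7 days, 65% at 30 and 75% at 60. A prewhitened version keeps the gradient (0.15 at 3 days, 0.95 at 60). For a second policy following another by 7, 14, 21 or 30 days, the ratio is 0.17, 0.29, 0.39 or 0.47.

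**4. What this does to weights.** The weight is 1/(SE² + tau²). In setting A the median reported SE is 0.0065 at 4 days and 0.0059 at 60; the true SDs are 0.037 and 0.009. Weight of a 4-day series relative to a 60-day one:

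- tau = 0: reported (0.0059/0.0065)² = 0.82; correct (0.009/0.037)² = 0.06.
- tau = 0.02: reported 0.000435/0.000442 = 0.98; correct 0.000481/0.001769 = 0.27.
- tau = 0.05: reported 0.002535/0.002542 = 1.00; correct 0.002581/0.003869 = 0.67.

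**5. Pooling, all lengths.** 100 municipalities at each of 5, 7, 10, 14, 21, 30, 45 and 60 days, 20 cases/day, DerSimonian-Laird, 200 repeats. A minimum of 14, 21 or 30 days leaves 500, 400 or 300 of the 800.

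| Minimum | Estimated tau at true 0 / 0.02 / 0.05 | SD of pooled effect at true 0 / 0.02 / 0.05 |
|---|---|---|
| none | 0.0215 / 0.0295 / 0.0544 | 0.00081 / 0.00109 / 0.00184 |
| 14 days | 0.0115 / 0.0232 / 0.0509 | 0.00052 / 0.00110 / 0.00232 |
| 21 days | 0.0091 / 0.0221 / 0.0508 | 0.00060 / 0.00117 / 0.00244 |
| 30 days | 0.0076 / 0.0214 / 0.0506 | 0.00048 / 0.00129 / 0.00294 |

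At true tau 0.02, tau-squared is overstated (0.0295/0.02)² = 2.2 times with no minimum and (0.0221/0.02)² = 1.2 times with 21 days. At true tau 0, I² is 0.96, 0.87, 0.82 and 0.77 down the rows.

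**6. Pooling, two lengths.** With 50 five-day and 50 thirty-day series, the short ones take 48–51% of the weight. At true tau 0.02, estimated tau is 0.028 with them and 0.021 without (20 cases/day), or 0.059 and 0.029 (5 cases/day). In one run at 20 cases/day, the pooled SD with the short series divided by that without them was 1.45 at tau 0, 1.21 at 0.01, 0.97 at 0.02, 0.85 at 0.03 and 0.73 at 0.05. In a further run it was 1.3–2.0 at tau 0 and 0.80–0.87 at tau 0.05.

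**The case against.** Most of the case on the other side stands, and it sets the limits of the point.

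- **Independent counts.** A reader might infer that weights fail for short baselines whatever the outcome. They do not on the planned path. With independent daily counts Durbin-Watson was below 1.5 in at most 3% of fits, so the Pearson-scaled error would apply. Its ratio to the true SD was 0.96–1.03 from 4 to 60 days, and short series then took 2% of the weight. The problem comes through the 7-day average.
- **Precision.** A reader might infer that short series always damage the pooled effect. The last figures in the working show the reverse from a tau of about 0.02/day at 20 cases/day. With 12-day rather than 5-day baselines the ratio was 0.86 even at tau 0. The null runs showed no bias in the pooled effect, and pooled coverage was 92–96%.
- **The I² trigger.** Short series are not the sole cause of passing 50%: with 30-day series alone and no true heterogeneity, I² was already 0.73–0.77 (0.95–0.96 with the short ones added).
- **Lag.** If the break moves by 7 days, a first case 5 days before enforcement gives about 12 pre-break points, not 5. The ratio there is about 0.3. The lag does not lengthen the segment between two policies, since both breaks move.
- **Clock.** Under the country clock, with 28 pre-policy days, most ratios were 0.7–1.4. The trouble there was leading zeros and bias, a different matter. Segments as short as 7 days between policies remain under either clock.
- **Realism.** A series starting at a local first case would not begin at 20×exp(−0.08×5) = 13 cases/day. The figures show the gradient and are not forecasts for these data.

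**Conclusion.** The point holds in a limited form. The SAP sets no minimum pre-policy period. On the planned smoothed outcome, Newey-West understates the error most where the segment is shortest (about 0.2, 0.3, 0.4 and 0.5 of the true SD at 5, 12, 21 and 30 days). The weights then come close to one per municipality, and the undeclared scatter enters the heterogeneity estimate. The overstatement of tau is material when true tau is around 0.02/day or less, more so at low counts, and small at 0.05 with 20 cases/day (0.0544 against 0.0508).

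This rests on assumed case levels, growth, bandwidth and tau. Splines, deaths and the reproduction number were not simulated. A reader might conclude that short-baseline municipalities must leave the primary pool. The evidence does not support that: once tau is moderate, exclusion costs precision. A pre-specified restricted analysis is the proportionate answer.

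**What to change.** 1. **Reconcile the start of the series** between *Timing of analyses and outcome assessments* and *Analysis methods*, since the clock decides how common short baselines are. If the country clock is kept, state whether days before a municipality's first case count as pre-policy days.
2. **Add to the sensitivity analyses:** the pooled effect, tau-squared and I² will also be reported for municipality-intervention pairs with at least 21 days before the lagged start of the intervention, and again with 14 and 30 days. Count the days from the start of the local series or from the previous intervention, whichever is later. Conclusions on heterogeneity (aim 2) must hold in this restricted set.
3. **Count the excluded pairs** in the flow diagram already planned under *Study population*.

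**Cost.** A few sentences in the SAP and one filter in the code. The restricted set omits policies enacted early in a local epidemic or soon after another policy, and its pooled interval may be wider. The 21-day cutoff is a convention, hence the repeats at 14 and 30. The restriction reduces the understatement but does not repair it: at 21 days the Newey-West error is still only about 0.4 of the true SD.

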In coefficient of interest at a second stage, we will pool the effects for each intervention -or combination of interventions- (i.e. the coefficient of interest  $\beta_{3j}$  from the local level regression) using a random-effects meta-analysis. This meta-analysis will provide information to obtain a pooled effect estimate and a measure of heterogeneity. We will use the  $I^2$  as a measure of heterogeneity.

If the heterogeneity is moderate or high ( $I^2$  higher than 50%), we will carry out a meta-regression to assess whether subnational level determinants can explain the observed heterogeneity. We will analyse the following covariates: (i) Population size, (ii) Population density, (iii) Proportion of population over 60 years old, as a proxy for age structure of the population, (iv) Household density, and (iv) Proportion of population with basic education, as a proxy of socioeconomic status.

The meta-regression has the effect size  $\widehat{\theta}_k$  of a first-stage regression  $k$  as the outcome, covariates  $x_{ik}$ , a fixed effect  $\rho_1 S_a$  for the second-tier level  $a$  (i.e. State or Region) and a random-effect  $\delta_2 N_b$  for the national level  $b$  and a fixed effect  $\rho_2 Y$  for the time of the year (quarterly periods)(equation 6). The equation includes two types of independent errors, where  $\varepsilon_k$  is the sampling error of the effect size and  $\varsigma_k$  is the random-effect error term.

$$(6) \theta_k = \gamma_1 x_{1k} + \dots + \gamma_n x_{nk} + \rho_1 S_a + \delta_2 N_b + \rho_2 Y + \varepsilon_k + \varsigma_k$$

These controls for higher levels of administration and time of the year will allow us to control for constant characteristics at the subnational and national level, as well as changes in the effectiveness throughout the pandemic.

We will carry out the following sensitivity analyses: (1) comparison of effect estimates using a 5-day and 10-day lag; (2) quasi-myopic analyses to control for anticipatory effects (if there is evidence of), and (3) placebo tests evaluating changes at times when no policy was implemented. In the analyses for the number of cases and time-varying R, we will run additional sensitivity analyses estimating the number of SARS-CoV-2 cases corrected by under-ascertainment derived from mortality statistics.

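### Each policy's pooled effect mixes introductions with and without earlier policies, so unless effects are additive on the log-slope scale it depends on the policy background, as does part of the heterogeneity

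*SAP*

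**What the plan says.** All of this is in the SAP under Analysis methods.

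- **Counterfactual.** "The counterfactual outcome is the projection of the trend in the period before the introduction of the intervention". For a later policy, that trend already carries the effect of any earlier policy still operating.
- **Combination rule.** "We will consider interventions implemented within a 7-day period as a combination of interventions, following previous studies". The handling of Assumption 2 repeats the rule: "We will explicitly incorporate co-occurring interventions in a seven-day period as a combination of interventions". Effects are estimated separately when policies are "separated by at least seven consecutive days and for a maximum period of 30 days".
- **First-stage fit.** Two descriptions are given. One is a joint model: "This method allows estimating simultaneously the effect of several interventions". The other suggests one regression per combination: "we expect to run 10,000 regressions multiplied by the number of combinations of interventions at each municipal level". Equation 5 has no interaction between policies.
- **Second stage.** "we will pool the effects for each intervention -or combination of interventions", the pooled quantity being the slope change β3j.
- **Meta-regression.** It runs only if I² exceeds 50%. "We will analyse the following covariates: (i) Population size, (ii) Population density", followed by age structure, household density and education, with state, country and quarter terms. No covariate describes policy history.
- **Sensitivity analyses.** These cover lag, anticipation, placebo dates and under-ascertainment, but not sequence.

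**The concern.** A combination is defined by how close the start dates are, not by which policies had already been introduced. A curfew enforced more than a week after a lockdown carries the same label as a curfew enforced where nothing preceded it. The first measures an increment over a trend that the lockdown may already have lowered; the second measures an effect against unrestricted spread. These are different contrasts, and the second stage averages them.

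Two things are at stake. Under aim 1, the Protocol (Statistical analysis) uses the pooled effects to judge whether any intervention worked. A policy's answer could depend on where in the sequence it usually came. Under aims 2 and 3, differing policy backgrounds add to the between-municipality variation that the study sets out to measure and explain, yet no covariate represents them. Staggered introduction is central to the design, which relies on variation in timing and place, and Protocol Table 1 lists step-wise partial lockdown among the interventions.

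**Working it through.** **The plan's own figure.** The only number tied to the seven-day rule is the maximum of 52 combinations. A full year gives 366/7 = 52.3. The plan's window, from the region's first case (26 February 2020, Protocol introduction) to 31 December 2020 (SAP, Timing of analyses), is 310 days, and 310/7 = 44.3. So 52 matches a full year rather than the window. This does not affect the present point.

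**Assumed inputs (none is in the documents).** Baseline log slope 0.08 per day. Policies A and B are identical, each worth -0.06 per day alone. They start at days 30 and 60 of a 90-day series. Both together are worth -0.12 (additive), -0.09 (sub-additive) or -0.06 (redundant). For each scenario 100 Poisson series were simulated and fitted with a segmented model of equation 5's form with Pearson scale, without splines or lag. Mean slope changes per day:

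| Scenario | First policy, joint fit | Second policy, joint fit | Second policy, own regression, pre-period from day 1 |
|---|---|---|---|
| Additive | -0.060 | -0.060 | -0.079 |
| Sub-additive | -0.060 | -0.030 | -0.049 |
| Redundant | -0.060 | 0.000 | -0.019 |

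**Pooling by label under the joint fit.** Let w be the share of municipalities where A came first, f the first-policy effect and s the second-policy effect. With weights equal to the shares, pooled A = w·f + (1-w)·s and pooled B = (1-w)·f + w·s. At w = 0.9:

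- Additive: A = B = -0.060.
- Sub-additive: A = 0.9(-0.060) + 0.1(-0.030) = -0.057; B = 0.1(-0.060) + 0.9(-0.030) = -0.033.
- Redundant: A = 0.9(-0.060) + 0.1(0) = -0.054; B = 0.1(-0.060) + 0.9(0) = -0.006.

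At w = 0.1 the values for A and B swap. Within a given background, A and B are equal by construction.

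**One regression per combination.** With the pre-period taken from day 1, the projected trend averages the slopes before and after the first policy, so the second policy absorbs part of the first one's effect. In the additive case the later policy then looks stronger (-0.079 against about -0.060), so order matters even under additivity. If the pre-period is limited to the preceding segment, the second-policy results return to the joint-fit values.

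**Is additivity a safe default?** Assume growth is k(R-1) and each policy multiplies R by (1-c). The first slope change is -kRc and the second is -kRc(1-c), a ratio of 1-c: 70% at c = 0.3 and 50% at c = 0.5. Policies that do not interact on R can therefore still be sub-additive on the slope.

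**Effect on heterogeneity.** Assume a curfew is worth -0.04 per day alone and -0.01 after a lockdown. With share w of municipalities already under lockdown, pooled = -0.04(1-w) - 0.01w, which gives -0.031, -0.022 and -0.016 at w = 0.3, 0.6 and 0.8. At w = 0.6, background alone contributes a between-municipality SD of 0.03·√(0.6·0.4) = 0.0147. If the curfew were worth -0.04 in both settings, the pooled value would be -0.04 at every w and this SD would be 0.

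**The case against.** The strongest reply is that the first stage does not ignore earlier policies. The joint model includes them, the counterfactual is openly the trend before each introduction, and an average of incremental effects over the settings in which policies were actually introduced is a legitimate estimand. Random effects allow those increments to differ, the quarter term partly stands in for order, and the dates and interventions in each period will be listed in an appendix. All of this is true, but it does not remove the point. The context is lost at pooling, the quarter term enters only the conditional meta-regression, a quarter spans about 13 seven-day blocks, and the appendix listing is not used in the pooling.

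Stronger readings are tempting, and the documents do not support them:

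- A reader might infer that first policies necessarily show a full effect and later ones only a residual. That needs sub-additive effects. The plan's second description of the fit can push the other way.
- A reader might infer a planned ranking of policies. No test between policies is specified; any comparison comes from reporting one pooled effect per policy.
- A reader might expect the extra heterogeneity to be credited to population size or density, on the premise that large, dense municipalities carry more policies. The documents do not say that they do.
- A reader might assume that policies in force on a given day can be derived from the data. The SAP commits only to enforcement dates and mentions no lifting dates.

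**Conclusion.** The point holds in conditional form. Pooling by label averages introductions with no earlier policy and introductions on top of earlier ones, and nothing in equation 5, equation 6 or the sensitivity analyses separates them. Under the joint fit, the pooled effect depends on the mix of earlier policies unless effects are additive on the log-slope scale. Under one regression per combination with a pre-period from day 1, it depends on order even then. Where effects differ by background, part of the heterogeneity under aims 2 and 3 is policy background.

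Neither direction nor size can be settled from the documents. The direction depends on how equation 5 is fitted, and every effect size above follows from assumed slopes, shares and interaction. The illustrations range from no difference between identical policies to -0.054 against -0.006. The change is worth making because it separates distinct contrasts at little cost, not because a bias of known size has been shown.

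**What to change.** 1. From the enforcement dates, derive for each municipality and intervention period (a) whether a total or partial lockdown had already been introduced and (b) how many other viral-spread policies had already been introduced before p. Where lifting dates are available, use in-force status instead.
2. In the second stage, report each intervention's pooled effect by background, whatever the I²: no earlier viral-spread policy, earlier policies without lockdown, and earlier lockdown. For lockdown itself, split by with or without earlier policies.
3. Add (a) and (b) to the covariates x in equation 6.
4. State that each effect is an increment over policies already introduced, and that pooled effects of different policies should not be compared without regard to background. Say also whether equation 5 is fitted jointly or once per combination, since the direction turns on it.

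**Cost.** SAP wording and two derived variables. Some intervention-by-background cells will be small or empty, with wider intervals. Enforcement dates alone do not show whether an earlier policy had been lifted, so without lifting dates the split describes policy history rather than policies in force.

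### The SAP describes one joint first-stage model but counts one regression per combination of interventions; following the count would credit policies seven or more days apart with each other's effects

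*SAP*

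**What the plan says.** All the relevant text is in the SAP, Analysis methods.

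- **Joint model.** "The model will include each of the interventions (either as single interventions or combinations of"), indexed j = 1 to J, and "This method allows estimating simultaneously the effect of several interventions".
- **One fit per combination.** Immediately after equation 5: "we expect to run 10,000 regressions multiplied by the number of combinations of interventions at each municipal level".
- **Equation 5.** It shows a single j, without a sum, and gives that j its own time variable and time coefficient as well as its own post and timepost terms.
- **Other policies.** "We will explicitly incorporate co-occurring interventions in a seven-day period as a combination of interventions". Effects are estimated separately when interventions are "separated by at least seven consecutive days and for a maximum period of 30 days".
- **Coding of a policy.** Under equation 1, post "equals one for every time point thereafter". For equation 5 the SAP says "The final model is an extension of the regression described in equation 1 with the specifications described above" and does not redefine post or timepost.

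The second stage then pools the slope change, beta3j, for each intervention or combination.

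**The concern.** The joint description and the regression count cannot both describe the primary first-stage model, and the equation does not decide between them. A programmer who works from the count would fit each combination alone.

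In such a fit the other policies are omitted. The first policy's post-period then contains the second policy, and the second policy's pre-trend mixes days before and after the first. Grouping deals only with policies inside the same seven days. Nothing outside a joint model deals with policies further apart. The common 7-day lag leaves the gaps unchanged, and the planned placebo tests use dates without a policy, so they do not target carry-over between real ones.

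The SAP itself lists concurrent policies as a threat to its second assumption. The first aim is the effect of the interventions, and pooling beta3j would carry a shared bias into that result.

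**Working it through.** **The plan's own figures.** The ceiling of 52 combinations is 365 / 7 = 52.1, rounded down. (The data window, from the region's first case on 26 February to 31 December 2020, is 310 days, or 310 / 7 = 44.3 periods; nothing below depends on this.) With C combinations per municipality the stated count is 10,000 × C: 20,000 at C = 2 and 520,000 at C = 52. A joint model needs 10,000 × 1 = 10,000 per outcome. The two agree only at C = 1.

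**Equation 5 read as a joint model.** It has 1 + 3J columns, so 10 for J = 3. Time is the same variable for every j, so three columns are identical and the rank is 10 - 2 = 8. The separate time coefficients cannot be identified. The beta3j remain estimable once the duplicates are dropped, so this is a fault of specification and not in itself a bias.

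**Separate fits, daily counts.** The documents give no effect sizes. Assumed inputs: noiseless Poisson mean, log growth 0.08 per day, first policy (A) at day 40, second policy (B) 7 to 21 days later, slope changes -0.05 (A) and -0.03 (B), no splines, data cut 30 days after the policy being fitted.

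- True slopes: 0.08 before A; 0.08 - 0.05 = 0.03 between A and B; 0.03 - 0.03 = 0.00 after B.
- A alone: the fitted post-slope lies between 0.03 and 0.00, so beta3 lies between -0.05 and -0.08. Fitted: -0.077 (gap 7) to -0.058 (gap 21).
- B alone: the fitted pre-slope lies between 0.08 and 0.03, so beta3 lies between -0.03 and -0.08. Fitted: -0.072 (gap 7) to -0.054 (gap 21).
- B with no effect: the same pre-slopes but a post-slope of 0.03, so -0.072 + 0.03 = -0.042 (gap 7) and -0.054 + 0.03 = -0.024 (gap 21).
- Joint fit: -0.050 and -0.030.

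The 30-day cut does not rescue separate fits. A later policy still enters when it starts within 30 days, which the seven-day rule allows, and an earlier policy stays in the later one's pre-period.

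**With Poisson noise and other assumed inputs** (120 days, baseline mean 20 per day, growth 0.05, A at day 31 with no effect, B at -0.06; 1,000 replicates per gap). Separate fits cut at 30 days give A -0.053, -0.036 and -0.017 at gaps of 7, 14 and 21 days, with false-positive rates of 100%, 100% and 95.6%. Joint fits, uncut, give 4.0%, 5.4% and 5.2%.

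**With splines** (same inputs, uncut, 300 replicates). At gap 14 the separate estimate for the ineffective A is -0.038 with 3 df and +0.077 with 5 df. At gap 7 with 5 df it is -0.002, with 5.3% false positives. Splines therefore change the bias, including its sign, without reliably removing it. Joint fits with splines stay near zero, with 3% to 7% false positives.

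**On the planned 7-day moving average** (first set of inputs, 120 days, trailing average assumed):

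| Gap | Joint A (true -0.05) | Joint B (true -0.03) | Ineffective B, joint | Ineffective B, separate |
|---|---|---|---|---|
| 7 days | -0.033 to -0.034 | -0.046 | -0.016 | -0.045 |
| 14 days | -0.044 to -0.045 | -0.035 | -0.005 | -0.035 |

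The short ranges reflect small differences in set-up between repeat calculations. Averaging smears each change over the following days, so some misattribution remains at short gaps even in a joint fit.

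**The case against.** The strongest reply is that the joint model is the intended one. Two sentences say so, the second stage refers to the local-level regression in the singular, and the contrary statement is a workload forecast that may loosely count coefficients. That stands as far as it goes: a reader might infer that the plan has committed to separate regressions, and the documents do not support that. But the forecast says regressions, and equation 5 does not correct it.

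A reader might also infer a flat contradiction between a post variable that stays at one and effects estimated "for a maximum period of 30 days". The documents do not support that either. The open-ended definition belongs to the generic equation 1, and the 30-day maximum reads naturally as a limit on follow-up. What remains is an omission: the SAP does not say whether data stop at 30 days, at the next policy, or otherwise.

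The objection that the illustration leaves out the planned splines is fair. It limits what can be said about size and sign, but the spline fits show the problem does not reliably go away.

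Finally, joint fitting costs precision. In 200 Poisson replicates (assumed mean about 14 per day at the policy date, gap 7), the standard deviation of the estimate for an ineffective second policy was 0.024 jointly against 0.006 separately on the averaged series, and 0.051 against 0.005 on daily counts. That cost is real, but the separate estimates are precise about the wrong value.

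**Conclusion.** The concern holds as an internal inconsistency in the primary first-stage model. Following the regression count gives misattributed effects; following equation 5 literally as a joint model gives a rank-deficient design.

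Under the stated assumptions, separate fits turn -0.05 and -0.03 per day into about -0.058 to -0.077 and -0.054 to -0.072, and give an ineffective second policy about -0.024 to -0.042. Effects, growth, gaps and series length are all assumed, and the SAP does not specify its splines. Only the existence of the bias is general.

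Two further inferences go too far. An ineffective later policy will not always look effective, because with splines the bias can vanish or reverse. Nor does a joint model recover the effects exactly: it does so on noiseless daily counts, but on the planned moving average some error remains at gaps of about 7 to 14 days.

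**What to change.** Write equation 5 as one Poisson model per municipality and outcome:

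ln E(Y_t) = beta0 + f(time_t) + sum over j of (beta2j × post_tj + beta3j × timepost_tj) + case-definition terms,

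where f is a single time trend that keeps the planned splines. In addition:

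- State that the 30-day maximum limits follow-up, and define for each j when post and timepost start and end (lag, 30-day limit, next policy).
- Restate the count as about 10,000 regressions per outcome.
- Acknowledge that the moving average leaves some smearing between policies about 7 to 14 days apart.

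This changes SAP wording and code only; no new data are needed. The statistical price is clearly wider intervals where policies lie close together: in the gap-7 example on the averaged series, 0.024 / 0.006 = 4 times the standard deviation.
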